7.8. Clinical Event Adjudication

7.8.1. Clinical Cardiovascular Events, Venous Thromboembolic Events and All Deaths

The identification of a potential clinical cardiovascular event, venous thrombo embolic event and all deaths will be made by the trial site or by Pfizer or designee. The site will communicate the event to Pfizer or designee within 24 hours of awareness of the potential clinical cardiovascular event using the appropriate CRF module.

Cardiovascular disease is a major cause of mortality for subjects with T2DM. In order to evaluate the cardiovascular safety of ertugliflozin and to meet regulatory requirements for the assessment of cardiovascular safety of any new diabetic therapy, serious cardiovascular events and all deaths will be adjudicated in this trial (including events from subjects who continue to be followed after discontinuation of investigational product), and across the Phase 2 and 3 ertugliflozin program. The Endpoint Adjudication Committee (EAC) will be comprised of an external panel of independent physicians experienced in assessing cardiovascular endpoints. The panel will be blinded to treatment assignments. The members of the EAC will not be an Investigator in any trial for ertugliflozin. The events to be adjudicated by the committee include:

1. All deaths.
2. Non-fatal myocardial infarction; hospitalization for chest pain or to rule out myocardial infarction, or other hospitalization due to suspected myocardial ischemia where myocardial infarction needs to be ruled out.
3. Non-fatal stroke (and all events that may be a stroke including all transient ischemic attack (TIA) events, reversible ischemic neurologic deficit (RIND) or other acute ischemic cerebrovascular event where stroke needs to be ruled out).
4. Hospitalization for unstable angina.
5. Hospitalization for heart failure.
6. Venous thromboembolism/pulmonary embolus.

The criteria to define clinical cardiovascular events will be detailed in the Endpoint Adjudication Committee charter. All potential clinical cardiovascular events will be collected from the first day of double-blind treatment through the end of study (including 14 day post-dose reporting period) for all randomized subjects who have received at least one dose of investigational product. The collection period will continue through study completion/end-of-study whether or not the subject continues to receive investigational product unless the subject is unwilling to be contacted by the personnel at the investigational site.

Clinical cardiovascular events occurring between the Screening visit (the time of informed consent) and double-blind treatment randomization will not be adjudicated as that subject will be excluded from the trial as per [Section 4.2](#).

090177e1848ce2dd\Approved\Approved On: 23-Sep-2013 15:48

Pfizer or designee will provide a listing of specific documents needed to support adjudication by the EAC. Obtaining documentation will be the responsibility of the trial site. Documentation will include, but is not limited to any of the following: hospital discharge summaries, operative reports, clinic notes, ECGs, diagnostic cardiac enzymes, results of other diagnostic tests, autopsy reports and death certificate information. The adjudication charter will contain additional information on source documents to be collected for event adjudication.

The composite of adjudicated events of cardiovascular death, non-fatal myocardial infarction, non-fatal stroke (often referred to as major cardiovascular events [MACE]), plus hospitalization for unstable angina will contribute to a meta-analysis of cardiovascular safety of ertugliflozin across the Phase 2 and 3 programs. Events of venous thromboembolism/pulmonary embolism and hospitalized congestive heart failure (CHF) will be separately tabulated across the Phase III clinical development program, and are not included in the cardiovascular composite of MACE plus hospitalized unstable angina.

7.8.2. Fractures

Spontaneously reported fractures will be adjudicated by an independent and blinded external fracture adjudication committee (FAC) comprised of radiologists. In the event that a subject experiences a clinical fracture during the trial, the radiographs and/or local radiologist report and other relevant documentation will be sent to the FAC. The FAC will review the radiograph(s) (if available) and, where applicable the local radiologist report and other source documents and confirm the presence of the fracture, location of fracture, number of fractures, and type of fracture (ie, high-trauma, low-trauma, pathological fracture, stress fracture, and other fracture). The FAC members will not be Investigators or sub-Investigators in any trial in the Phase 3 program and they will be blinded to the subject's assigned treatment group. A FAC charter will describe the precise mandates and procedures to be used for the adjudication of clinical fractures.

7.8.3. Pancreatitis

Type 2 diabetes is a risk factor for pancreatitis. As part of the overall assessment of the safety profile of ertugliflozin, events of pancreatitis reported in this trial and throughout the Phase 3 program will be adjudicated by an independent external panel of physicians experienced in assessing pancreatic disease. The panel will be blinded to treatment assignment. A Pancreatitis Adjudication Charter will describe the precise mandates and procedures to be used for the adjudication of pancreatitis.

7.8.4. Liver Injury

As hepatic safety is a significant issue in drug development, all events that meet pre-specified criteria for potentially important hepatotoxicity will be adjudicated by an external independent panel of physicians experienced in assessing liver injury. The panel will be blinded to treatment assignment and will assess causality. A Liver Injury Adjudication Charter will describe the precise mandates and procedures to be used for assessing liver injury and assigning causality.

090177e1848ce2dd\Approved\Approved On: 23-Sep-2013 15:48

7.8.5. Acute Renal Failure

Ertugliflozin, an SGLT2 inhibitor, increases urinary glucose excretion leading to an osmotic diuresis, and has the potential to reduce estimated glomerular filtration rate (eGFR). As part of the overall assessment of renal safety, events reported in this trial and throughout the Phase 3 program that meet pre-specified criteria for potentially important renal failure events will be adjudicated by an external independent panel of physicians experienced in adjudication of renal events. The panel will be blinded to treatment assignment and will assess causality. A Renal Failure Adjudication Charter will describe the precise mandates and procedures to be used for assessing renal failure and assigning causality.

8. ADVERSE EVENT REPORTING

8.1. Assessing and Recording Adverse Events

An adverse event is defined as any untoward medical occurrence in a patient or clinical investigation subject administered a pharmaceutical product and which does not necessarily have to have a causal relationship with this treatment. An adverse event can therefore be any unfavourable and unintended sign (including an abnormal laboratory finding, for example), symptom, or disease temporally associated with the use of a medicinal product or protocol-specified procedure, whether or not considered related to the medicinal product or protocol-specified procedure. Any worsening (ie, any clinically significant adverse change in frequency and/or intensity) of a preexisting condition that is temporally associated with the use of the Sponsor's product, is also an adverse event.

Changes resulting from normal growth and development that do not vary significantly in frequency or severity from expected levels are not to be considered adverse events. Examples of this may include, but are not limited to, teething, typical crying in infants and children and onset of menses or menopause occurring at a physiologically appropriate time.

Sponsor's product includes any pharmaceutical product, biological product, device, diagnostic agent or protocol-specified procedure, whether investigational (including placebo or active comparator medication) or marketed, manufactured by, licensed by, provided by or distributed by the Sponsor for human use.

Adverse events may occur during the course of the use of the Sponsor's product in clinical trials or within the follow-up period specified by the protocol, or prescribed in clinical practice, from overdose (whether accidental or intentional), from abuse and from withdrawal.

Adverse events may also occur in screened subjects during any pre-allocation baseline period as a result of a protocol-specified intervention, including washout or discontinuation of usual therapy, diet, placebo treatment or a procedure.

All adverse events will be recorded from the time the consent form is signed through 14 days following cessation of treatment and at each examination on the Adverse Event case report forms/worksheets.

090177e1848ce2dd\Approved\Approved On: 23-Sep-2013 15:48

8.2. Definition of an Overdose for This Protocol and Reporting of Overdose to the Sponsor

In this trial, an overdose is any dose higher than 100 mg/day of ertugliflozin or matching placebo or any dose higher than 25 mg/day of ertugliflozin or matching placebo for more than 14 days.

If an adverse event(s) is associated with (“results from”) the overdose of Sponsor's product or vaccine, the adverse event(s) is reported as a serious adverse event, even if no other seriousness criteria are met.

If a dose of Sponsor's product or vaccine meeting the protocol definition of overdose is taken without any associated clinical symptoms or abnormal laboratory results, the overdose is reported as a non-serious Event of Clinical Interest (ECI), using the terminology “accidental or intentional overdose without adverse effect.”

All reports of overdose with and without an adverse event must be reported within 24 hours to Pfizer or designee either by electronic media or paper. Appropriate contact information can be found in the Investigator Trial File Binder (or equivalent).

8.3. Reporting of Pregnancy and Lactation to the Sponsor

Although pregnancy and lactation are not considered adverse events, it is the responsibility of Investigators or their designees to report any pregnancy or lactation in a subject (spontaneously reported to them) that occurs during the trial or within 14 days of completing the trial. All subjects who become pregnant must be followed to the completion/termination of the pregnancy. Pregnancy outcomes of spontaneous abortion, missed abortion, benign hydatidiform mole, blighted ovum, fetal death, intrauterine death, miscarriage and stillbirth must be reported as serious events (Important Medical Events). If the pregnancy continues to term, the outcome (health of infant) must also be reported.

Such events must be reported within 24 hours to Pfizer or designee either by electronic media or paper. Appropriate contact information can be found in the Investigator Trial File Binder (or equivalent).

8.4. Immediate Reporting of Adverse Events to the Sponsor

8.4.1. Serious Adverse Events

A serious adverse event is any adverse event occurring at any dose or during any use of Sponsor's product that:

- Results in death;
- Is life threatening;
- Results in persistent or significant disability/incapacity;
- Results in or prolongs an existing inpatient hospitalization;

- Is a congenital anomaly/birth defect;
- Is a cancer;
- Is associated with an overdose;
- Is another important medical event.

Refer to [Table 6](#) for additional details regarding each of the above criteria.

Any serious adverse event, or follow up to a serious adverse event, including death due to any cause that occurs to any subject from the time the consent is signed through 14 days following cessation of treatment, whether or not related to the Sponsor's product, must be reported within 24 hours to Pfizer or designee either by electronic media or paper. Appropriate contact information can be found in the Investigator Trial File Binder (or equivalent).

Additionally, any serious adverse event, considered by an Investigator who is a qualified physician to be related to the Sponsor's product that is brought to the attention of the Investigator at any time outside of the time period specified in the previous paragraph also must be reported immediately to Pfizer or designee.

All subjects with serious adverse events must be followed up for outcome.

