- d. ET = Early termination, subjects who discontinue taking investigational product prematurely should complete procedures for the ET visit and have a 2-week follow-up phone call from their last dose of investigational product. In addition, if subjects agree, they will also be contacted via telephone by the Investigator/qualified designee according to the same schedule as if the subjects were still taking investigational product to assess for SAEs and to collect information on clinical events per [Section 7.8](#), if applicable. See [Section 6.7](#) for additional details.
- e. Each randomized subject should have a follow-up phone call 14 ±3 days after the last dose of investigational product to assess for SAEs and to collect information on clinical events per [Section 7.8](#), if applicable.
- f. Subjects who require glycemic rescue therapy per [Section 5.6](#) must have rescue therapy initiated at either a scheduled or unscheduled visit, and not by a telephone call.
- g. Brief physical examination includes assessment of heart, lungs, abdomen, extremities and skin.
- h. Sitting triplicate blood pressure and pulse rate should be collected, as instructed in [Section 7.4.2](#).
- i. Duplicate measurements of supine and standing blood pressure and pulse rate should be taken per [Section 7.4.3](#). Postural changes should only be collected at the Rescue Visit if the Rescue Visit occurs in Phase A.
- j. S2 ECG is read locally at investigative site. ECG for all other time points should be submitted to be read centrally.
- k. Screening DXA scans should be performed at Visit S3 or at least ten days before Day 1 visit. In case of discontinuation of investigational product during Phase A, a DXA scan will be performed if the discontinuation occurs between Week 12 and Week 26. In case of discontinuation of investigational product during Phase B, a DXA scan will be performed if the discontinuation occurs at least 12 weeks from the previous scan. See [Section 7.6](#) for additional details.
- l. Routinely collected urinalysis samples will be sent to the central laboratory for dipstick analysis (not including glucose assessment) and microscopy if dipstick is positive for blood, nitrites, leukocytes and/or protein.

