090177e1848ce2dd\Approved\Approved On: 23-Sep-2013 15:48

were observed following 12 weeks of dosing with ertugliflozin. There was a suggestion of changes in markers of bone resorption, though there did not appear to be a clear dose-dependent effect with increasing dose of ertugliflozin. In totality, the clinical relevance of these findings remains unclear. However, the effect of ertugliflozin on BMD will be evaluated in this trial, and all clinical fractures will be adjudicated throughout the Phase 3 program by an independent committee and will be included in a pooled analysis.

In the clinical program to date, no clinically significant changes from baseline in serum aminotransferases (ALT and AST) have been observed.

Phase 3 clinical trial data from another SGLT2 inhibitor, dapagliflozin, revealed a numerical imbalance in the rates of breast and bladder cancer in dapagliflozin-treated subjects compared to control.¹¹ The causal relationship to dapagliflozin for this finding is uncertain given the small number of events and the absence of any preclinical signal (ie, no reported increase in either tumor in carcinogenicity studies) with dapagliflozin. Moreover, in the larger clinical program of another SGLT2 inhibitor, canagliflozin, no cancer imbalance, including in breast or bladder cancer events, was reported. Because thorough evaluation of malignancies is important in the development program of all investigational medications, detailed information will be collected for subjects who develop a malignancy. This information could include but is not limited to relevant medical history, biopsy, or operative reports, etc.

Complete information for this compound may be found in the Single Reference Safety Document (SRSD), which for this study is the Investigators' Brochure for ertugliflozin (PF-04971729).

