2.2.2. Secondary Endpoints

- Change in FPG from Baseline to Week 26.
- Change in body weight from Baseline to Week 26.
- Incidence of HbA1c of <7% (53 mmol/mol) at Week 26.
- Change in systolic and diastolic blood pressure from Baseline to Week 26.
- Change in HbA1c, FPG, and body weight from Baseline to Weeks 52 and 104.
- Incidence of HbA1c <7% (53 mmol/mol) at Weeks 52 and 104.
- Incidence of HbA1c ≤6.5% (48 mmol/mol) at Weeks 26, 52 and 104.
- Change in systolic and diastolic blood pressure from Baseline to Weeks 52 and 104.
- Proportion of subjects requiring glycemic rescue therapy up to Weeks 26, 52 and 104.

- Time to glycemic rescue therapy up to Weeks 26, 52 and 104.
- Endpoints related to pharmacokinetics of ertugliflozin.

Secondary endpoints related to bone safety are:

- Change in BMD as measured by DXA at the lumbar spine (L₁-L₄), femoral neck, total hip and distal forearm from Baseline to Week 26.
- Change in BMD as measured by DXA at the lumbar spine (L₁-L₄), femoral neck, total hip and distal forearm from Baseline to Weeks 52 and 104.
- Change from baseline in bone biomarkers at Weeks 26, 52 and 104.

As part of a large Phase 3 program for ertugliflozin, this protocol will contribute safety data to a program-wide meta-analysis of clinical cardiovascular events. Additional detail is provided in [Section 7.8.1](#).

To maintain the ability of the trial to provide information on long-term safety data, subjects who discontinue investigational product and do not withdraw consent will thereafter be contacted via telephone by the Investigator/qualified designee according to the same schedule as if the subject were still taking investigational product (ie, according to [Section the Schedule of Activities](#) and [Section 6](#)). Such subjects will be asked to return to the clinic at the time of the Week 104 visit. Additional details are provided in [Section 6.7](#).

This trial will utilize an external Data Monitoring Committee (E-DMC) to periodically review safety data.

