6.7. Subject Withdrawal

Subjects may withdraw from the trial at any time at their own request, or they may be withdrawn at any time at the discretion of the Investigator or sponsor for safety or behavioral reasons, or the inability of the subject to comply with the protocol required schedule of study visits or procedures at a given study site.

If a subject does not return for a scheduled visit, every effort should be made to contact the subject. For withdrawn subjects, the Investigator should inquire about the reason for withdrawal, request the subject return all unused investigational product, request the subject to return for an early termination visit, and follow up with the subject regarding any unresolved adverse events (AEs).

If the subject withdraws from the trial, and also withdraws consent for disclosure of future information, no further evaluations should be performed, and no additional data should be collected. The sponsor may retain and continue to use any data collected before such withdrawal of consent.

If a subject indicates his or her intention to stop active participation (ie, chooses to no longer attend visits at the investigational site, take blinded investigational product, and have other study-related procedures conducted at the investigational site) in the trial or if the Investigator has recommended stopping the investigational product, the Investigator must clarify with the subject if he/she is willing to continue in the study with contact at intervals to provide a brief and focused update on health status (eg, SAEs and events eligible for adjudication [see [Section 7.8](#)]). It will be important for the subject to understand the importance of complete collection of information, and also the limited requirements for continuing to provide this information (ie, a brief telephone contact, occurring at the time of the originally planned study visits). Thus, subjects may discontinue study drug and continue in the study with clinic visits or allow continued site contacts without clinic visits, or they may indicate that they do not wish to have further contact with the site.

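### Off-drug subjects are contacted to Week 104 to assess for SAEs, but the recording and reporting rules end 14 days after treatment, leaving no clear duty for later SAEs rated unrelated, cancers included

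*Combined protocol and SAP*

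**What the plan says.** Follow-up after stopping drug. Footnote d of the Schedule of Activities says that subjects who stop investigational product early are, if they agree, telephoned "according to the same schedule as if the subjects were still taking investigational product to assess for SAEs" and, as a further purpose, to collect the clinical events of Section 7.8. Section 6.7 describes the contact as "a brief and focused update on health status (eg, SAEs and events eligible for adjudication", again naming SAEs apart from adjudicated events. Section 2.2.2 gives the aim: "To maintain the ability of the trial to provide information on long-term safety data". It also sets the end point: "Such subjects will be asked to return to the clinic at the time of the Week 104 visit".

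Recording and reporting. Section 8.1 states: "All adverse events will be recorded from the time the consent form is signed through 14 days following cessation of treatment". Section 8.4.1 requires 24-hour reporting of any SAE, related or not, "from the time the consent is signed through 14 days following cessation of treatment". An SAE that the investigator considers related and that comes to light "at any time outside of the time period specified in the previous paragraph also must be reported immediately to Pfizer or designee". Section 8.8 says that all events meeting SAE criteria go to the sponsor within 24 hours of the site hearing of them, with no time limit. It cites 8.4.1 and adds that it leaves investigator duties as they are.

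Cancer. Section 8.4.1 makes every cancer an SAE. Section 1.4 describes a numerical imbalance in breast and bladder cancer with another drug of the class, of uncertain cause, and undertakes that "detailed information will be collected for subjects who develop a malignancy".

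**The concern.** The calls and the reporting rules do not fit together. A site is told to ask an off-drug subject about SAEs for up to two years. The sections that say what to do with the answer close the causality-independent window 14 days after treatment. A site that follows 8.1 and 8.4.1 would hear of a cancer on a planned call, rate it unrelated, and have no stated duty to record or report it. A site that follows footnote d, 6.7 or the literal words of 8.8 would send it in.

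What is at stake is the long-term safety data. A treatment imbalance in cancers shows only if cases are captured evenly, whatever the opinion on each one. The exception for related events is a weak safeguard. The causality guidance in Table 6 weighs time course and directs a rating of no relationship when the timing is not reasonable or another cause is obvious, so a blinded investigator may readily rate a cancer found months after the last dose as unrelated. The external data monitoring committee, which under 8.8 is to review all SAEs, can see only those that reach the sponsor. The primary HbA1c analysis is not touched.

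**Working it through.** This is mainly a reconciliation of text. The plan states no figure to reproduce.

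**Step 1: which off-drug events have a rule more than 14 days after the last dose?** Cessation of treatment is read as the last dose of investigational product, in line with the 14-day call in Section 6.5 and footnote e.

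| Event after day 14 off drug | Asked about? | Duty to record or report |
|---|---|---|
| Death, cardiovascular event, venous thromboembolism | Yes (footnote d, 6.7, 7.8.1) | Yes: 7.8.1 collects to end of study, on or off drug, whatever the causality |
| Fracture, pancreatitis, liver injury, renal failure | Yes, through footnote d's reference to 7.8 | 7.8.2 to 7.8.5 provide for adjudication but state no off-drug window |
| Any other SAE, rated related | Yes (footnote d, 6.7) | Yes: 8.4.1, second reporting paragraph |
| Any other SAE, rated unrelated, including cancer | Yes (footnote d, 6.7) | None in 8.1 or 8.4.1; 8.8 only if read literally |

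The last row is the gap. Cancer falls in it because Section 7.8 does not list it as an adjudicated event type. The undertaking in 1.4 gives neither a time window nor a collection route.

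**Step 2: does 8.8 close it?** Read as a restatement of 8.4.1, which its cross-reference and disclaimer suggest, it inherits the 14-day limit. Read literally, it requires what 8.4.1 does not. On the first reading the gap stays. On the second, the two sections contradict each other. Either way they need reconciling.

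**Step 3: how long is the gap for one subject?** Inputs: follow-up ends at Week 104 (2.2.2), and 14 days, or 2 weeks, are covered after the last dose (8.1, 8.4.1).

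Gap in weeks = 104 − (week of last dose + 2)

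- Stop just after Day 1: 104 − 2 = 102
- Stop at Week 12: 104 − 14 = 90
- Stop at Week 26: 104 − 28 = 76
- Stop at Week 52: 104 − 54 = 50
- Stop at Week 78: 104 − 80 = 24

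**Step 4: how much of the trial's patient-time could it be?** The documents give no rate of stopping drug with continued follow-up. The 15% and 20% loss rates in Sections 3 and 9.1 concern missing BMD and HbA1c data at Week 26 and are not such a rate. As an illustration only, assume that a fraction p of subjects stops at Week t and that all of them accept contact to Week 104:

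Share of planned time = p × (104 − (t + 2)) / 104

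- p = 0.15, t = 52: 0.15 × 50 / 104 = 7.2%
- p = 0.30, t = 40: 0.30 × 62 / 104 = 17.9%

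Both p and t are assumptions. The result is patient-time, not a count of missed events.

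**The case against.** The best defence is that this is loose wording and that no data need be lost. Section 8.4.1 sits under a heading on immediate reporting. One could read the plan as expedited reporting to 14 days plus ordinary collection of SAEs at later contacts. Section 6.7 stresses complete information, 8.8 has no time limit on its face, and 1.4 undertakes to gather details on malignancies without a window.

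Much of this stands. A reader might infer that late SAEs rated unrelated are excluded or may not be reported. The documents do not say so: nothing forbids it, and 8.8 read literally requires it. A reader might also infer that the plan ignores off-drug cancers. It does not: 1.4 shows the intent to collect, and what is missing is the route. Section 2.2.2 should not be cited as naming SAEs either, because it speaks only of long-term safety data. The SAE purpose comes from footnote d and 6.7.

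The defence does not dispose of the point. The reading that splits expedited reporting from later collection runs into 8.1, which closes recording, and not only fast reporting, at 14 days.

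Two further objections have weight. Off-drug subjects may start other therapies, including ones previously prohibited (6.7, 6.7.2), so late events are harder to attribute. And Section 9 leaves detailed analysis methods to a separate SAP, so the lack of an off-drug SAE table in 9.3 is not in itself a demonstrated omission.

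**Conclusion.** The point holds as a conflict between sections, at minor severity. Footnote d and 6.7 have sites ask about SAEs to Week 104. Sections 8.1 and 8.4.1 state no duty to record or report those rated unrelated after day 14 off drug, and 8.8 either repeats that limit or contradicts it. Capture of such events, cancers above all, then depends on which section a site follows and on the causality rating.

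Per subject the gap is 76 weeks for a stop at Week 26 and 50 weeks for a stop at Week 52, reading cessation of treatment as the last dose. How many subjects or events this affects cannot be derived from the documents. A reader might take the 7.2% to 17.9% illustration as the share of safety data that will be lost. That is not supported: the discontinuation rates and timing are assumed, subjects may decline further contact (6.7, 6.7.2), and deaths, cardiovascular events and venous thromboembolism remain collected throughout under 7.8.1.

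**What to change.** In Sections 8.1 and 8.4.1, add a sentence along these lines: for subjects who have stopped investigational product and remain in contact, every SAE the site learns of up to the Week 104 contact, cancers included, is recorded and reported to the sponsor whatever its causality rating. Align 8.8 with that sentence, and have footnote d and 6.7 refer to it.

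In Section 9.3, or in the SAP with a pointer from 9.3, tabulate SAEs twice: on treatment, to 14 days after last dose, and through end of follow-up. The on-treatment table answers the worry that therapies started off drug confound late events.

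The cost is a few sentences, one extra table and some additional SAE forms. The contacts are already scheduled, so no visit or call is added.
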